11.2 Pain Assessments

Pain will be assessed with the OMDQ Question 2 (mouth and throat soreness or MTS), which will be completed daily from baseline until oral mucositis assessment grade 0 or 1. The OMDQ is provided in [Appendix D](#). The OMDQ will be provided in booklets for patient distribution during Combination Treatment and Mucositis Observation Follow-up.

11.3 Analgesic Use

Patients often require analgesics, including opioids for pain control. Patients will record any analgesic use, including name, dose, and frequency of dose, in the OMDQ Booklet. Information from the source documents and the diary will be recorded into the EDC system as a concomitant medication. Analgesics will be converted to morphine equivalents at the time of data analysis.

11.4 Other Assessments

Frequency and duration of interruptions in radiation therapy will be recorded.

11.5 Tumor Assessments

Tumor assessments will be performed according to the schedule of assessments. The patient's tumor response will be assessed using RECIST v1.1 [Eisenhauer et al. 2009] until progression, start of next therapy or until end of Long Term Follow-up, whichever comes first [Appendix B]. When measurable disease is not present (e.g. post-operative patients), RECIST v1.1 assessment is not performed until measurable disease presents (this is considered progression and no further assessments will be done) or start of next therapy. Tumor status information will be collected and will include disease progression, and survival. During the follow up period, data will be collected at standard of care intervals, i.e., month 3 (\pm 7 days) and also at months 6, 9 and 12 (each \pm 14 days) following the last day of combination therapy to document start date of subsequent therapies.

12 ASSESSMENT OF SAFETY

The safety of RRx-001 will be assessed through collection and analyses of adverse events (AEs) and laboratory tests.

12.1 Specification of Safety Variables

Safety assessments will consist of monitoring and reporting adverse events (AEs) and serious adverse events (SAEs) that are considered related to RRx-001, cisplatin or radiation therapy, all events of death, and any study specific issue of concern.

12.1.1 Adverse Events

An adverse event (AE) is defined as any new untoward medical occurrence or worsening of a pre-existing medical condition in a patient or clinical investigation patient administered an investigational (medicinal) product and that does not necessarily have a causal relationship with this treatment. An AE can therefore be any unfavorable or unintended sign (including abnormal laboratory finding, for example), symptom or disease temporally associated with the use of investigational product, whether or not considered related to the investigational product.

This includes the following:

- AEs not previously observed in the patient that emerge during the protocol specified AE reporting period, including signs or symptoms associated with SCC that were not present prior to the AE reporting period.
- Complications that occur as a result of protocol-mandated interventions (e.g., invasive procedures such as biopsies).
- Preexisting medical conditions (other than the condition being studied) judged by the investigator to have worsened in severity or frequency or changed in character during the protocol-specified AE reporting period.
- Clinical progression of SCC should not be reported as an AE.

12.1.2 Serious Adverse Events

An AE should be classified as an SAE if:

- It results in death (i.e., the AE actually causes or leads to death).
- It is life threatening (i.e., the AE, in the view of the investigator, places the patient at immediate risk of death. It does not include an AE that, had it occurred in a more severe form, might have caused death.).
- It requires or prolongs inpatient hospitalization.
- It results in persistent or significant disability/incapacity (i.e., the AE results in substantial disruption of the patient's ability to conduct normal life functions).
- It results in a congenital anomaly/birth defect in a neonate/infant born to a mother exposed to the investigational product.
- It is considered a significant medical event by the investigator based on medical judgment (e.g., may jeopardize the patient or may require medical/surgical intervention to prevent one of the outcomes listed above).

All AEs that do not meet any of the criteria for serious should be regarded as non-serious AEs.

The terms "severe" and "serious" are not synonymous. Severity (or intensity) refers to the grade of a specific AE, e.g., mild (Grade 1), moderate (Grade 2), or severe (Grade 3) myocardial infarction. "Serious" is a regulatory definition (see previous definition) and is based on patient or event outcome or action criteria usually associated with events that pose a threat to a patient's life or functioning. Seriousness (not severity) serves as the guide for defining regulatory reporting obligations from the Sponsor to applicable regulatory authorities.

Severity and seriousness should be independently assessed when recording AEs and SAEs into the EDC system.

12.2 Methods and Timing for Assessing and Recording Safety Variables

The investigator is responsible for ensuring that all AEs and SAEs that are observed or reported during the study are collected and reported to the FDA, IRB, and EpicentRx, Inc. in accordance with CFR 312.32 (IND Safety reporting).

12.2.1 Adverse Event Reporting Period

The study period during which all AEs and SAEs must be reported begins after informed consent is obtained and ends 30 days following the last administration of study treatment (RRx-001, cisplatin and radiation therapy) or study discontinuation/termination, whichever is earlier. After this period, investigators should only report SAEs that are attributed to prior study treatment.

12.2.2 Assessment of Adverse Events

Investigators will assess the occurrence of AEs and SAEs at all patient evaluation time points during the study. All AEs and SAEs whether volunteered by the patient, discovered by study

personnel during questioning, or detected through physical examination, laboratory test, or other means will be recorded in the patient's medical record and into the EDC system.

Each recorded AE or SAE will be described by its duration (i.e., start and end dates), severity, regulatory seriousness criteria if applicable, suspected relationship to the investigational product (see following guidance), and actions taken.

The AE grading (severity) scale found in the National Cancer Institute Common Terminology Criteria for Adverse Events (NCI-CTCAE), Version 5.0, will be used for AE reporting.

Table 4: Adverse Event Grading (Severity) Scale

Grade	Severity	Alternate Description ^a
1	Mild (apply event-specific NCI-CTCAE grading criteria)	Transient or mild discomfort (< 48 hours); no interference with the patient's daily activities; no medical intervention/therapy required
2	Moderate (apply event-specific NCI-CTCAE grading criteria)	Mild to moderate interference with the patient's daily activities; no or minimal medical intervention/therapy required
3	Severe (apply event-specific NCI-CTCAE grading criteria)	Considerable interference with the patient's daily activities; medical intervention/therapy required; hospitalization possible
4	Very severe, life threatening, or disabling (apply event-specific NCI-CTCAE grading criteria)	Extreme limitation in activity; significant medical intervention/therapy required, hospitalization probable
5	Death related to AE	

Note: Regardless of severity, some events may also meet regulatory serious criteria. Refer to definitions of an SAE

^aUse these alternative definitions for Grade 1, 2, 3, and 4 events when the observed or reported AE is not in the NCI-CTCAE listing.

To ensure consistency of AE and SAE causality assessments, investigators should apply the following general guideline:

- **YES**

There is a plausible temporal relationship between the onset of the AE and administration of the investigational product (RRx-001), and the AE cannot be readily explained by the patient's clinical state, intercurrent illness, or concomitant therapies; and/or the AE follows a known pattern of response to the investigational product (RRx-001); and/or the AE abates or resolves upon discontinuation of the investigational product (RRx-001) or dose reduction and, if applicable, reappears upon re-challenge.

- **NO**

Evidence exists that the AE has an etiology other than the investigational product (RRx-001) (e.g., preexisting medical condition, underlying disease, intercurrent illness, or concomitant medication); and/or the AE has no plausible temporal relationship to administration of the investigational product (RRx-001) (e.g., cancer diagnosed 2 days after first dose of study drug).

Expected adverse events are those adverse events that are listed or characterized in the Product Label or current Investigator Brochure.

Unexpected adverse events are those not listed in the Product Label or current Investigator Brochure or not identified. This includes adverse events for which the specific or severity is not consistent with the previous description.

12.2.3 Specific Instructions for Recording Adverse Events

Investigators are strongly encouraged to use correct medical terminology/concepts when reporting AEs or SAEs and to avoid colloquialisms and abbreviations.

a. Deaths

All deaths that occur during the protocol-specified AE reporting period, regardless of attribution, will be reported to the appropriate parties. When recording a death, the event or condition that caused or contributed to the fatal outcome should be reported as the single medical concept. If the cause of death is unknown and cannot be ascertained at the time of reporting, report “Unexplained Death”.

b. Preexisting Medical Conditions

A preexisting medical condition is one that is present at the start of the study. Such conditions should be reported as medical and surgical history. A preexisting medical condition should be re-assessed throughout the trial and reported as an AE or SAE only if the frequency, severity, or character of the condition worsens during the study. When reporting such events, it is important to convey the concept that the preexisting condition has changed by including applicable descriptors (e.g., “more frequent headaches”).

c. Hospitalizations for Medical or Surgical Procedures

Any AE that results in hospitalization or prolonged hospitalization should be documented and reported as an SAE. If a patient is hospitalized to undergo a medical or surgical procedure as a result of an AE, the event responsible for the procedure, not the procedure itself, should be reported as the SAE. For example, if a patient is hospitalized to undergo coronary bypass surgery, record the heart condition that necessitated the bypass as the SAE.

Hospitalizations for the following reasons do not require reporting:

- Hospitalization or prolonged hospitalization for diagnostic or elective surgical procedures for preexisting conditions
- Hospitalization or prolonged hospitalization required to allow efficacy measurement for the study or
- Hospitalization or prolonged hospitalization for scheduled therapy of the target disease of the study.

d. Pregnancy

If a female patient becomes pregnant while receiving investigational therapy or within 90 days after the last dose of study drug, a report should be completed and expeditiously submitted to the EpicentRx, Inc. Follow-up to obtain the outcome of the pregnancy should also occur. Abortion,

whether accidental, therapeutic, or spontaneous, should always be classified as serious, and expeditiously reported as an SAE. Similarly, any congenital anomaly/birth defect in a child born to a female patient exposed to the investigational product should be reported as an SAE.

e. Post-Study Adverse Events

The investigator should expeditiously report any SAE occurring after a patient has completed or discontinued study participation if attributed to prior investigational product exposure. If the investigator should become aware of the development of cancer or a congenital anomaly in a subsequently conceived offspring of a female patient who participated in the study, this should be reported as an SAE.

12.3 Reporting Requirements for Adverse Events

12.3.1 Expedited Reporting Requirements for Serious Adverse Events

All SAEs are required to be reported to the Sponsor on the SAE CRF within 24 hours of a site's knowledge of the SAE. Please send all SAE reports to:

[contact] or [contact]

The Medical Monitor, [name], can be reached at [contact] (cell) or [contact] should any questions arise regarding an SAE or SAE reporting.

Relevant follow-up information should be submitted to EpicentRx's Drug Safety as soon as it becomes available and/or upon request.

Occasionally, EpicentRx may contact the reporter for additional information, clarification or current status of the patient for whom an adverse event was reported. For questions regarding SAE reporting, you may contact the EpicentRx [Medical Contact](#) (re: page 1).

12.3.2 Routine Reporting of Adverse Events

- The Institutional Review Board (IRB) should be notified per local guidelines.

12.4 Type and Duration of Follow-Up of Patients After Adverse Events

All AEs and SAEs that are encountered during the protocol-specified AE reporting period that are considered at least possibly related to the study drug should be followed to their resolutions, or until the investigator assesses them as stable, or the patient is lost to follow-up. Resolution of AEs and SAEs (with dates) should be documented on the appropriate AE CRF page and in the patient's medical record to facilitate source data verification.

For some SAEs, the Sponsor or its designee may follow-up by telephone, fax, electronic mail, and/or a monitoring visit to obtain additional case details deemed necessary to appropriately evaluate the SAE report (e.g., hospital discharge summary, consultant report, or autopsy report).

13 STATISTICAL METHODS

13.1 Sample Size

A sample size of 40 patients is considered adequate for this POC study to explore the radioprotective potential of RRx-001 and identify a safe regimen for further development.

With 10 patients per group, the study will have approximately 80% power to detect a 75% reduction in the average number of days with severe OM (from 24 to 6 days) at the two-sided 5% significance level; this calculation is based on Student's t-test and assumes the standard deviation for duration of severe OM is 13 days. While not powered for more modest treatment effects, the study will yield important safety information and trends in efficacy data to inform decisions about future study designs.

13.2 Efficacy Analysis

Statistical methods for the calculation and analysis of efficacy endpoints are provided below. Limited hypothesis-testing will be performed, as this is a small POC study. All statistical analyses are exploratory.

Duration of Severe Oral Mucositis (SOM): The duration of SOM (WHO grade 3 or 4) will be calculated as the number of days from the onset of SOM (first time a WHO grade 3 or 4 is observed) to the day when severe OM has resolved (first time WHO grade 2 or less is observed after last WHO grade 3 or 4). Durations of 0 will be assigned to patients who do not experience severe OM. Any patient who dies or withdraws prior to resolution of severe OM will be assumed to have severe OM for the remainder of the observation period. All available OM assessments will be used to derive efficacy endpoints, including WHO grades recorded during the treatment and follow-up period in order to capture resolution of OM.

The duration of SOM will be compared for each of the 3 RRx-001 regimens versus the untreated control group using the Wilcoxon rank-sum test. This rank-based test does not depend on normality assumptions for these small sample sizes. All patients randomized (the intent-to-treat population) will be used for this analysis.

Time to onset of SOM: The number of days from the start of chemotherapy until the date of first OM assessment grade 3 or 4 will be listed and summarized descriptively for each treatment group.

Incidence of SOM: The incidence of SOM (WHO grade 3 or 4) will be calculated as the number of patients with at least one OM WHO grade 3 or 4, divided by the number patients in the treatment group. Patients with no OM assessments will be assumed to have severe scores. Patients who die or withdraw without experiencing OM grade 3 or 4 will also be assumed to have severe scores. The incidence of SOM will be compared between each RRx-001 group and the control arm using Fisher's Exact test. Clopper-Pearson two-sided 95% confidence limits will be calculated for the proportion of patients with SOM in each treatment arm.

Duration and incidence of ulcerative OM: The duration of ulcerative OM (WHO grade 2, 3, and 4) will be calculated in a manner similar to duration of severe OM. That is, the duration of ulcerative OM will be calculated as the number of days from the onset of ulcerative OM (first time a WHO grade 2, 3, or 4 is observed) to the day when ulcerative OM has resolved (first time WHO grade 0 or 1 is observed after last WHO grade 2, 3 or 4). A similar imputation scheme will be used in the event that patients die or withdraw prior to resolution of OM to grade 0 or 1. The Wilcoxon rank-sum tests will be used to compare treatment groups. Incidence of ulcerative OM will be calculated and analyzed as described above for severe OM.

Patient-reported pain: The average of patient-reported mouth and throat soreness (MTS) scores, graded on a scale from 0 (no soreness) to 4 (extreme soreness), will be summarized by treatment group during each study week and displayed graphically. The number of patients with scores of 0 or 1 will be enumerated by time and treatment group.

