2 STUDY SUMMARY

Title	PREVLAR: A Phase 2a Randomized, Parallel Group, Open-Label, Multicenter Study to Assess the Safety and Efficacy of Different Schedules of RRx-001 in the Attenuation of Oral Mucositis in Patients Receiving Concomitant Chemoradiation for the Treatment of Locally Advanced Squamous Cell Carcinomas of the Oral Cavity or Oropharynx
Phase	Phase 2a
Patient Population	Pathologically-confirmed diagnosis of squamous cell carcinoma (SCC) of the oral cavity or oropharynx planned to be treated with cisplatin plus concurrent IMRT Note: Patients with unknown HPV positive primary tumors (SCC) whose treatment plan matches the requirements specified in Inclusion Criteria #2 below are eligible for the trial
Objectives	Safety: To assess the safety and tolerability of varying dosing schedules of RRx-001 during treatment and for 28 days following end of IMRT. To assess the long-term effect of RRx-001 on tumor response to standard concomitant chemoradiation. Efficacy: To assess the efficacy of RRx-001 in the attenuation of severe oral mucositis (SOM) in patients receiving cisplatin and radiation therapy for the treatment cancers of the oral cavity or oropharynx.
Number of Patients	Approximately 40 evaluable patients

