Study Design	This is a Phase 2a, randomized, open-label, parallel group trial to assess the safety and efficacy of three schedules of RRx-001 compared to standard of care in patients receiving a standard regimen of tri-weekly cisplatin plus concomitant IMRT in patients being treated for cancers of the oral cavity or oropharynx. Patients meeting the eligibility criteria and consenting to participate will be randomized 1:1:1:1 to one of the three regimens of RRx-001 or a control (~10 patients per arm) with 1 stratification factor (two levels: oral cavity or oropharynx): Arm 1: "RRx-001 Pre-Treatment + SOC Chemoradiation" Two infusions of RRx-001 will be given each week during the two weeks prior to the start of chemoradiation (four doses total). No additional RRx-001 will be given during chemoradiation. Arm 2: "RRx-001 Pre-Treatment + 2 Concurrent Doses + SOC Chemoradiation" Two infusions of RRx-001 will be given each week during the two weeks prior to the start of chemoradiation. In addition, one dose of RRx-001 will be given on the last radiation day in each of weeks 2 and 5 during chemoradiation Arm 3: "RRx-001 Pre-Treatment + 6 Concurrent Doses + SOC Chemoradiation" Two infusions of RRx-001 will be given each week during the two weeks prior to the start of chemoradiation. In addition, one dose of RRx-001 will be given on the last radiation day of each of the first 6 weeks during chemoradiation Arm 4: "SOC Chemoradiation Only (Control)" No doses of RRx-001 will be administered. Patients assigned to this arm will receive only standard of care chemoradiation

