
Eligibility Criteria (Inclusion and Exclusion)
	
Inclusion Criteria
 
 1. Pathologically confirmed diagnosis of squamous cell carcinoma (SCC) of the oral cavity and oropharynx Note: Patients with unknown primary tumors whose treatment plan matches the requirements specified in Inclusion Criterion #2 below are eligible for the trial 2. Treatment planned to include standard cisplatin monotherapy administered either every three weeks (100 mg/m² for 3 doses) or weekly (40 mg/m² for 7 doses) with concomitant radiation delivered as a continuous course of IMRT with single daily fractions of 2.0 to 2.2 Gy with a cumulative radiation dose between 60 Gy and 72 Gy. Planned radiation treatment fields must include at least two oral sites (buccal mucosa, floor of mouth, tongue, soft palate) that are each planned to receive a total of > 55 Gy. Patients who have had prior surgery are eligible, provided they have fully recovered from surgery, and patients who may have surgery in the future are eligible. 3. ECOG performance status ≤ 2. 4. Participants must have adequate organ and marrow function as defined below: 
 A. Absolute neutrophil count (ANC) $\geq 1,500$ / mm³ B. Platelets $\geq 100,000$ / mm³ C. Hemoglobin ≥ 9.0 g/dL 5. Adequate renal and liver function as indicated by: 
 A. Serum creatinine acceptable for treatment with cisplatin per institutional guidelines) B. Total bilirubin ≤ 1.5 x upper-normal limit (ULN) C. Aspartate aminotransferase (AST) and alanine aminotransferase (ALT) ≤ 2.5 x ULN D. Alkaline phosphatase ≤ 2.5 x ULN

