--	---

Statistical Methods
	
Safety Endpoints:
 
 • Incidence of adverse events, including serious adverse events (SAEs) and clinically significant laboratory abnormalities. • Overall tumor response to treatment using RECIST or site preference criteria. 
Efficacy Endpoints:
 
 • Duration (in days) of severe oral mucositis (SOM, WHO grades 3 or 4) • Time (in days) to onset of SOM • Incidence of SOM • Incidence and duration of ulcerative mucositis (WHO grades 2, 3, 4) • Patient-reported mucositis pain as measured by question 2 of the Oral Mucositis Daily Questionnaire 
Design:
 
This is a randomized, open-label, parallel group, Phase 2 study to assess the safety and radioprotective potential of RRx-001 in patients undergoing chemoradiation therapy for locally advanced head and neck cancer.
 
A total of approximately 40 patients will participate in this study. All patients will receive standard chemoradiation therapy consisting of cisplatin either every three weeks (100 mg/m² for 3 doses) or weekly (40 mg/m² for 7 doses) + radiotherapy (IMRT) administered daily (except weekends) for 7 weeks. In conjunction with this “standard of care” (SOC), patients will be randomly assigned to receive one of 3 regimens of RRx-001 or a control (no treatment).
 
Sample Size:
 
A sample size of approximately 40 patients (~10 per group) is considered adequate for this proof-of-concept (POC) study to explore the radioprotective potential of RRx-001 and identify a safe regimen for further development.
 
Statistical Methods:
 
Efficacy and safety data will be summarized using descriptive statistics, including the mean, standard deviations, median, minimum and maximum for continuous endpoints and frequency tables for categorical data.
 
Efficacy Analysis:
 
Hypothesis testing of efficacy endpoints will be performed for exploratory purposes only. For continuous efficacy endpoints, non-parametric methods will be used to compare each RRx-001 group to the untreated control group (Wilcoxon rank-sum tests). Fisher’s exact test will be used to evaluate treatment differences for binary outcomes. Two-sided 95% confidence intervals will be calculated for proportions using the Clopper-Pearson method.
 
Safety Analysis:
 
Safety data, including adverse events (AEs), serious adverse events (SAEs), ECOG performance status, clinical laboratory tests, vital signs and physical examination results will be listed and summarized descriptively by treatment group. Adverse events will be coded by system organ class (SOC) and preferred term using MedDRA (Version 18.1), and severity will be based on NCI CTCAE Grade criterion (Version 5.0).
 
Descriptive statistics (sample size, mean, median, standard deviation, quartiles and range) and graphical methods (longitudinal plots) will be used to present change from pre-treatment values in laboratory parameters during the treatment period. The incidence of febrile neutropenia, bacterial infections, grade 3 or 4 cervicofacial dermatitis, and other toxicities of clinical interest (xerostomia, trismus, fatigue, weight loss, radiation dermatitis, and dysgeusia) will be tabulated by treatment arm.

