Patients with radiation-induced mucositis generally show highly consistent clinical courses. Concomitant chemotherapy increases both the risk and severity of mucositis. Signs and symptoms typically begin by the completion of the first week of treatment (cumulative radiation dose of 10 Gy) and consist primarily of mucosal erythema and symptoms akin to a burned mouth from hot food or drink that are easily controlled with standard OTC pain medications. At cumulative radiation doses of 20 Gy to 30 Gy, the integrity of the mucosa breaks down and mucosal ulcerations that are usually limited to the movable mucosa (the more keratinized epithelium of the hard palate, dorsal tongue and gingiva are unaffected), occur. Unlike common oral ulcers like aphthous stomatitis, the ulcers associated with mucositis are irregular, deep and disproportionately painful, requiring more aggressive symptom management such as the use of narcotic analgesia. Ulceration severity usually peaks at radiation doses of around 50 Gy (end of week 5). The lesions expand and become confluent. Breakthrough pain, even with morphine or fentanyl is not uncommon. Lesions typically heal spontaneously after 2-4 weeks following the cessation of radiation therapy.

A variety of scales are used to assess mucositis severity, of these, the WHO scale is the most consistent and widely used. This scale, which has been effectively used in clinical trials, is based on a combination of functional (ability to eat) and objective (presence of ulceration or erythema) criteria. WHO scores correlate with patient-reported outcomes, analgesic use and resource use. Other available scales include RTOG and NCI-CTCv5, which have evolved to contain elements that are similar to WHO criteria.

Concepts of the pathogenesis of mucositis have undergone dramatic revisions from Sonis' original hypothesis in 1998 of epithelial injury due to direct clonogenic cell death of epithelial

stem cells to a complex biologic process involving oxidative stress and immune activation that culminates in epithelial apoptosis, atrophy, ulceration and healing [[Sonis 1998](#)].

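### Randomization is stratified by tumour site but no efficacy test uses site; if site matters for mucositis, the exploratory tests lose some power that stratified tests would recover cheaply

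*Combined protocol and SAP*

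**What the plan says.** The Study Summary (Study Design) and section 6.1 both describe randomization to four arms of about 10 patients, "with 1 stratification factor (two levels: oral cavity or oropharynx").

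Section 13.2 then sets out the efficacy comparisons, each RRx-001 arm against control:

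- Duration of severe oral mucositis (SOM): "The duration of SOM will be compared for each of the 3 RRx-001 regimens versus the untreated control group using the Wilcoxon rank-sum test".
- Incidence of SOM: "The incidence of SOM will be compared between each RRx-001 group and the control arm using Fisher's Exact test".
- Duration of ulcerative mucositis: "The Wilcoxon rank-sum tests will be used to compare treatment groups"; its incidence is handled as for SOM.

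The Study Summary repeats these methods and qualifies them: "Hypothesis testing of efficacy endpoints will be performed for exploratory purposes only". Neither section 13 nor the Study Summary contains a stratified test, a site covariate or a summary by site. The power calculation in section 13.1 is a two-sample t-test with no site term.

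On eligibility, the Study Summary admits "Patients with unknown HPV positive primary tumors (SCC") when the treatment plan fits. It does not say in which of the two strata they are randomized.

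**The concern.** Site is the only factor the sponsor chose to balance, and the usual reason for such a choice is that the factor may affect outcome. If it does, balancing on site and then ignoring it leaves the between-site variation in the comparison. The arms are more alike than the test assumes, so the true type I error falls below 5% and power is lost.

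This matters more here than in a large trial. Section 13.1 claims about 80% power only for a fall from 24 to 6 days and concedes that smaller effects are not powered. What is at stake is the sensitivity of exploratory p-values that will inform the next study's design. The validity of a conclusion is not in question.

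**Working it through.** **Inputs from the plan (section 13.1).** 10 per group, means 24 and 6 days (difference 18), SD 13, two-sided 5%.

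**The plan's own figure.** The noncentrality is 18 / (13 × √(2/10)) = 18 / 5.81 = 3.10 on 18 degrees of freedom. Exact t-test power is 83.3% at 10 per group and 78.7% at 9. Ten is therefore the smallest group size that reaches 80%, and the plan's approximate 80% is reproduced on the conservative side.

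**Assumed inputs.** The documents give neither the effect of site on mucositis nor the expected site mix. The smaller stratum was taken as 2, 3 or 5 of 10 in each arm, and the gap between sites in mean SOM days as 0, 5, 10, 13 or 20. Total SD was held at 13, so with p the share in one site and g the gap:

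- share of variance due to site = p(1 − p)g² / 169;
- within-site SD = √(169 − p(1 − p)g²).

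For example, at g = 10 the share is 0.16 × 100/169 = 9% for a 2:8 split and 0.25 × 100/169 = 15% for 5:5.

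**Duration of SOM.** The exact Wilcoxon test was compared with the exact van Elteren test (stratum weights 1/(N + 1)), using 40,000 simulated trials per case with normal durations and an 18-day effect:

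| Site gap (days) | Variance due to site | Unstratified power | Stratified power | Difference (points) |
|---|---|---|---|---|
| 0 | 0% | 79% | 77–79% | −2.1 to −0.4 |
| 5 | 2–4% | 79% | 79–80% | −0.6 to +0.5 |
| 10 | 9–15% | 80% | 83–84% | +2.6 to +3.7 |
| 13 | 16–25% | 81% | 85–88% | +4.7 to +7.0 |
| 20 | 38–59% | 83–84% | 94–99% | +10 to +16 |

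Unstratified type I error is 2.9–3.5% at a 10-day gap and 2.0–2.9% at 13 days. The stratified test stays at 4.3–5.0%.

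**Variations on the duration result.**

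- *Durations floored at 0 and rounded to whole days* (about 34% zeros in the treated arm): −2.5 to −1.8 points at no gap, −1.6 to −0.7 at 5 days, +1.9 to +3.2 at 10 and +3.9 to +6.3 at 13.
- *Uncorrected normal approximations instead of exact p-values*: −4.6 to −2.9 at no gap, 0 to +1.1 at 10 days and +2.1 to +4.3 at 13.
- *A 12-day treatment effect*, exact tests: 45% v 44–46% at no gap, 44% v 49–50% at 10 days and 42–44% v 52–55% at 13.
- *One patient's difference in site mix between arms* (2 v 3 or 4 v 5), 10-day gap: unstratified power is 75% or 84% depending on direction, against 82–85% stratified. Averaged over direction, the gain is 2.7 to 4.6 points at 10 days and 5.6 to 8.3 at 13, with a loss of 0.6 to 1.4 at no gap.

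**Incidence of SOM.** Full enumeration, 10 per arm, Fisher against an exact conditional stratified test. The control and treated rates are assumptions.

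| Control v treated | Site gap | Fisher power | Stratified power |
|---|---|---|---|
| 80% v 20% | none | 63.5% | 64–65% |
| 70% v 20% | none | 42.6% | 43–44% |
| 80% v 20% | 20 percentage points | 63.6% | 66–67% |
| 70% v 20% | 20 percentage points | 42% | 45–46% |

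With a 70% rate in both arms, type I error is 1.0–1.2% for Fisher and 1.2–1.5% for the stratified test.

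**The case against.** The strongest reply is that nothing here is an error. The tests are valid and declared exploratory, and no go/no-go rule hangs on p < 0.05. Balancing on a factor and then using a simple exact or rank test in a 10 v 10 comparison is a defensible choice. That stands.

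The benefit also depends wholly on an assumed site gap, and the documents hint that it may be small. Section 3.1 states: "Patients with radiation-induced mucositis generally show highly consistent clinical courses". Inclusion criterion 2 narrows field variation in every patient: "Planned radiation treatment fields must include at least two oral sites", each planned for more than 55 Gy. That stands too. Break-even with exact tests is at about 5 days. With normal approximations it is nearer 10 days, which is over 40% of the assumed 24-day control mean (10/24 = 42%), and the plan does not say which kind of p-value it will use.

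The middle-case gain is modest as well. At 10 days it is worth less than one patient per arm, since going from 9 to 10 per group adds 83.3 − 78.7 = 4.6 points. The largest gains need a 20-day gap that no document supports. One could therefore keep the planned tests as the main analysis and add stratified ones as sensitivity analyses. That is a reasonable lesser option.

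These points limit the importance of the concern but do not remove it. Exact or permutation p-values keep the downside to about 2.5 points at equal splits, and the stratified incidence test cost nothing in the cases computed. Stratified randomization protects against site imbalance, but with strata this small a difference of one patient between arms can still occur, and the unstratified test does not correct for it.

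**Conclusion.** The concern holds as a conditional point about efficiency. Site is the sole stratification factor and no planned efficacy test uses it. Type I error is not inflated.

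For SOM duration at the plan's 18-day effect, stratifying with exact p-values costs 0.4 to 2.1 points if site is irrelevant (up to 2.5 with floored, tied data). It is about neutral at a 5-day gap, gains 2.6 to 3.7 points at 10 days and gains 4.7 to 7.0 at 13 days. For a 12-day effect the gain at 13 days is larger, at about 42–44% v 52–55%.

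These figures rest on an assumed site gap, an assumed site mix and, except in the floored version, normal durations. Whether site is strongly prognostic cannot be settled from the documents. The change is worth considering but is not required for a sound analysis. The unassigned stratum for unknown primaries is a separate missing detail and adds nothing to the power argument.

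**What to change.** In section 13.2, pre-specify site-stratified comparisons for both severe and ulcerative mucositis:

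- van Elteren test for duration, with p-values obtained by permuting within strata;
- an exact stratified test of the Cochran-Mantel-Haenszel type for incidence;
- for every patient, the stratum recorded at randomization;
- the unstratified Wilcoxon and Fisher tests as sensitivity analyses, and as the fallback if a stratum is empty in one of the two arms compared.

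State in the randomization description which stratum patients with unknown primaries enter.

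The cost is some SAP wording and a different procedure call, since site is already recorded for randomization. If site turns out to be unrelated to SOM, the duration test gives up about 0 to 2.5 points of power with exact or permutation p-values. The loss is about 3 points if two arms split 1 v 3 on site, and up to about 4.6 points at equal splits if normal approximations are used instead, which is the reason to specify permutation p-values. The exact stratified incidence test lost no power in the cases computed.
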